Study protocol: In this double-blind, placebocontrolled, crossover study, each subject will undergo 3 phases, the order of which will be randomized by a simple randomization scheme. The 3 phases will be Placebo (PBO), Citric Acid (CitA), and Potassium Citrate (KCit). Each phase will be 1 week in duration, during which subjects will take assigned study medications. A 1-week washout period is imposed between phases (Figure 1). During the first 2 days of each phase, subjects will be instructed to adhere to a diet at home with a daily composition of 800 mg calcium, 100 mEq sodium, 800 mg phosphorus, 50 mEq potassium

and 2 liters of total fluids daily. On the last 5 days of each phase, subjects will be kept on a constant metabolic diet of the same composition provided by the Clinical Research Unit (CRU). During the final two study days (days 6-7), subjects will be admitted to the CRU where a 22-hr urine and 2-hr fasting urine will be collected on day 6 under mineral oil to measure urine chemistries (stone risk factors) and acid-base parameters, and on day 7 for crystallization studies. Fasting blood will be obtained at the end of each urine collection.

Study Medications: Subjects will receive three 10 mEq tablets of CitA twice a day during the CitA phase (60 mEq/day), two 10 mEq KCit tablets and one placebo tablet twice a day during the KCit phase (40 mEq/day), and 3 tablets twice daily of matching placebo during the PBO phase. Study tablets are prepared by a compounding pharmacy, with placebo tablets similar in appearance and size to the active medication tablets.

Sample size: This was calculated based on our preliminary studies. 20 subjects will provide a power of 0.80 at the 0.015 level of significance (to adjust for multiple comparisons of the three phases) to detect a difference of 0.3 units in CPR brushite, between treatment and placebo phases (within subject standard deviation of 0.38). Assuming 20% withdrawal, 25 subjects will be enrolled with the expectation that 20 subjects will complete the entire study.

Serum: Blood will be collected for measurement of serum sodium, potassium, chloride, CO₂, glucose, BUN, creatinine, calcium, albumin, magnesium, phosphorus, and uric acid. These will be measured primarily to assure subject safety (e.g. hyperkalemia, renal insufficiency, metabolic acidosis/alkalosis).

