24-hr urine stone risk factors: These are well established at the UT Southwestern Mineral Metabolism Laboratories:⁸ urine pH, citrate, calcium, phosphorus, oxalate, uric acid, ammonium, sulfate, chloride, sodium, potassium, magnesium, total volume, creatinine, TA, HCO₃⁻. These parameters will be combined to calculate saturation by JESS and compared individually across phases.

Saturation: Urine saturation will be directly measured by CPR as previously described⁹, and will be calculated from the measured urinary parameters by JESS as Saturation Index^{1, 2, 10}.

Additional physicochemical measures: In addition to CPR, we will assess *crystal growth (CG)* of brushite after seeding urine with a small amount of brushite (0.25 mg/ml urine) as previously described¹¹. We will also measure overall activity of urinary promoters and inhibitors to brushite crystallization as *formation product (FP)*. This will be based on an established method to assess the limit of metastability of brushite¹². FP is obtained by adding increasing amount of Ca to a series of aliquots of urine at constant pH for 2hrs, and is identified by the point at which visible brushite precipitation is elicited. Calculated SI using [Ca] and [P] at that point represents FP brushite. Measurement of CG and FP brushite will provide additional insights on the effects of KCit and CitA on CaP stone formation beside their effect on saturation, since the process of kidney stone formation depends on the complex interplay between these three factors.

Statistical Analysis: For each phase, descriptive statistics will be computed for continuous variables. Data transformation or nonparametric tests will be utilized as

needed to meet analysis assumptions. For this crossover design, repeated measures analysis will be implemented to assess treatment effects for biochemical parameters¹³. A Bonferroni-Hochberg adjustment will be used to adjust for multiple testing¹⁴. A mixed model approach will be used so that the covariance structure can be specified. If necessary,

	Urine			Brushite		
	Cit	pН	Ca	CPR / SI	CG	FP
CitA	↑	\leftrightarrow	\leftrightarrow	\rightarrow	\rightarrow	↑
KCit	↑	1	\downarrow	$\leftrightarrow/\downarrow$	↓	↑

Expected changes (↔, ↑, or ↓) compared with placebo IRB # 032012-058 pairwise multiple comparisons will be made with with contrasts derived from the repeated measures models.

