- b. Citric Acid 10 mEq 2 pills + Placebo 1 pill, 3 times a day
- c. Citric Acid 10 mEq, 3 pills 3 times a day

A 1-week washout period is imposed between phases (Figure 1). During the first 4 days of each phase, subjects will be instructed to adhere to a diet at home with a daily composition of 800 mg calcium, 100 mEq sodium, 800 mg phosphorus, 50 mEq potassium and 2 liters of total fluids daily. On the last 3 days of each phase, subjects will be kept on a constant metabolic diet of the same composition provided by the Clinical Research Unit (CRU). During the final two study days (days 6-7), subjects will collect a 24 hour urine at home on day 6 for crystallization studies, and also under mineral oil on day 7 to measure urine chemistries (stone risk factors) and acid-base parameters. The subjects will bring the urine to the Mineral Metabolism Clinic at Aston on the morning of day 8. Fasting blood will be obtained in the Mineral Metabolism Clinic on day 8 during this visit.

The rationale for the adjustment in medication dose/frequency is that the data we have so far collected in the pilot study seems to suggest that the dose of citric acid used previously in Aim 1 does not significantly raise urine citrate as we had hypothesized. Some of the possibilities are: 1. medication doses given twice a day are not frequent enough (hence looking at the scheme in b. above) or, 2. the total dose given was not sufficient (hence the scheme c above), or that patients with Calcium Phosphate stones do not respond to Citric Acid the same way that healthy individuals without stones respond.

Aim 1c Outpatient Study:

Aim 1c of this protocol also represents an extension of Aim 1. Aim 1c is a pilot project which proposes a lower dose of potassium citrate over the three phases of the study.

Subjects: - Aim 1c will recruit up to five patients with calcium phosphate stones CaP with or without hypercalciuria, and five normal healthy subjects without kidney stones.

Inclusion criteria: CaP Stone Former with elevated urinary pH will be >25 years, of either gender and any race and ethnicity. CaP stone disease will be defined based on the most recent available stone composition with CaP constituting over 70% of overall stone components.

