Exclusion criteria: History of recurrent urinary tract infections, chronic diarrhea, estimated eGFR <60 ml/min and chronic use of non-steroidal anti-inflammatory drugs, angiotensin 2 receptor blocker, ACE-inhibitors, diuretics, antacids, alkali treatment and carbonic anhydrase inhibitors.

Study protocol: In this double-blind, placebo-controlled, crossover study, each subject will undergo 3 phases, the order of which will be randomized by a simple randomization scheme. In this aim, we will utilize the following medications during the 3 phases:

- a. Control, no medication
- b. Potassium Citrate 5mEq 1 pill, 2 times a day
- c. Potassium Citrate 10mEq, 1 pill, 2 times a day

In each phase, the subjects will be instructed to adhere to a diet on a instructed diet consisting of 800 mg calcium, 800 mg phosphorus, 100 mEq of sodium, 50 mEq of potassium and 2 liters of fluids daily at home. On the third day of the study, while on the instructed diet the subjects will collect 24-hour urine at home for the kidney stone risk profiles. The subjects will bring the urine to the Mineral Metabolism Clinic at Aston, 9th floor on the morning of day 4.

The rationale for the adjustment in medication dose/frequency of the Potassium Citrate is evidenced in the recently completed three phases of the study control, potassium citrate and citric acid in calcium phosphate stone formers. The results of the study showed that the rise in urinary citrate (an inhibitor of CaP crystallization) with potassium citrate supplementation was negated with a significant elevation in urinary pH resulting in increased urinary supersaturation with CaP salts. In this aim, we are proposing a lower dose of potassium citrate sufficient enough to raise the urinary citrate modestly, while does not alter the urinary pH to negate the protective inhibitory effect of urinary citrate.

Aim 2: Calcium phosphate stone formers with hypercalciuria

Rationale: Since the majority of CaP stone formers are hypercalciuric (60-80%), we will separately study this group with a similar 3-phase design. In our practice, these patients are all prescribed a thiazide diuretic (generally indapamide due to its long half-life, allowing once a day dosing) to reduce hypercalciuria along with a potassium supplement to avert thiazide-induced hypokalemia¹⁹. However, it is unclear whether KCl or KCit is the optimal K supplement for CaP stone formers on a thiazide diuretic.

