Study protocol: In this double-blind, placebo-controlled crossover study, each hypercalciuric CaP stone former will undergo 3 phases, the order of which will be randomized by a simple randomization scheme. The 3 phases will be Indapamide+KCI+PBO, Indapamide+KCI+CitA, and Indapamide+KCit+PBO. The dose of indapamide will be fixed at 1.25 mg/day in each subject, the amount of potassium provided as KCit or KCI will be kept constant at 20 mEq BID, and the amount of Citrate provided either as KCit or CitA will be 20 mEq BID (Table 2). This will allow for direct assessment of effects of KCI vs. KCI+CitA vs. KCit. During the first 4 days of each phase, subjects will be instructed to adhere to a diet at home with a daily composition of 800 mg calcium, 100 mEq sodium, 800 mg phosphorus, 50 mEq potassium and 2 liters of total fluids daily. On the last 3 days of each phase, subjects will be kept on a constant metabolic diet of the same composition provided by the Clinical Research Unit (CRU). During the final two study days (days 6-7), subjects will collect a 24 hour urine at home on day 6 for crystallization studies, and also under mineral oil on day 7 to measure urine chemistries (stone risk factors) and acid-base parameters. The subjects will bring the urine to the Mineral Metabolism Clinic at Aston on the morning of day 8. Fasting blood will be obtained in the Mineral Metabolism Clinic on day 8 during this visit.

Protection of Human Subjects

1. 1. Risks to the Subjects

Human Subjects Involvement and Characteristics

Aim 1

3-phase, double-blind, cross-over metabolic study examining the effects of potassium citrate and citric acid on urinary predictors of stone formation in calcium phosphate stone formers *without* hypercalciuria

Disease State	Subject Number	Inclusion Criteria	Exclusion Criteria
Calcium phosphate stone formers without hypercalciuria	25	 ≥ 21 years of age for all subjects Stone analysis showing calcium phosphate as major component of stone (>70%) Hypocitraturia (urine citrate < 320 mg/d) 24hr urine pH>6.40 	 Hypercalciuria (24h urine calcium > 250 mg/day) Recurrent urinary tract infections Chronic diarrhea Endogenous creatinine clearance < 70ml/minute by eGFR Chronic use of non-steroidal anti-inflammatory drugs, angiotensin 2 receptor blockers, ACE inhibitors, diuretics, antacids/alkali treatment, or carbonic anhydrase inhibitors

Aim 2

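### Aim 1c: if period is fitted or phases drift, simple randomisation of phase order in groups of at most five costs some precision that a pre-drawn list of distinct orders would keep (optional refinement)

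*Combined protocol and SAP*

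**What the plan says.** The Aim 1c study protocol paragraph sets the phase order by simple randomisation: "the order of which will be randomized by a simple randomization scheme. In this aim, we will utilize the following medications". The three phases are a control without medication and two potassium citrate doses. The Subjects paragraph sets the size: "Aim 1c will recruit up to five patients with calcium phosphate stones CaP with or without hypercalciuria, and five normal healthy subjects". No blocking, Latin square, fixed list of orders or separate list per group is described, and the term simple is not defined.

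Aim 1c is described as exploratory: "Aim 1c is a pilot project which proposes a lower dose of potassium citrate over the three phases of the study". It has no power statement, standard deviation, target effect or analysis paragraph of its own. The nearest analysis text is in Aim 1, Statistical Analysis: "For this crossover design, repeated measures analysis will be implemented to assess treatment effects for biochemical parameters". That paragraph goes on to a mixed model with pairwise contrasts, and it neither names nor rules out a period term. The only attrition figure is in Aim 1, Sample size: "Assuming 20% withdrawal, 25 subjects will be enrolled with the expectation that 20 subjects will complete the entire study".

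**The concern.** In a three-phase crossover, each treatment should appear about equally often in each phase. With five independent draws from six orders this often fails.

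- **If period is fitted**, the imbalance inflates the variance of the treatment contrasts. In the extreme case one treatment falls in the same phase for all five subjects, and in a group analysed alone its contrasts with the other treatments cannot then be separated from period.
- **If period is not fitted**, any drift between phases goes into the error of the contrasts.

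At stake is precision only. Aim 1c looks for a modest rise in urine citrate without a change in urine pH. These are small contrasts in very small groups, so avoidable error is worth removing when that is cheap.

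**Working it through.** **Inputs.** From the Aim 1c text: three phases (hence six orders), simple randomisation, n = 5 per group. Aim 1c contains no calculated figure to reproduce. The 20% withdrawal comes from Aim 1 (20/(1 − 0.20) = 25, as stated there), and applying it to Aim 1c is an assumption. Assumed as well: independent draws from the six orders; equal residual variance σ² in all subjects; and, for the shared-period case, the same period effect in both groups. The documents give no drift figure, so a range is shown.

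**Benchmark.** With perfectly balanced orders a pairwise contrast in a group of n has variance 2σ²/n, that is 0.400σ² at n = 5. The ratios below are relative to this, averaged over the pairwise contrasts, with non-estimable allocations counted separately and left out of the means.

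**1. Group analysed alone, period fitted.** Let N be the 3 × 3 count of treatments by phase. After subject and period are fitted, the information on treatment contrasts is nI − NN′/n.

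- *Five distinct orders.* All six orders give a count of 2 in every cell, and leaving one out removes a permutation matrix. On contrasts NN′ reduces to I, so the information is 5 − 1/5 = 4.8 and the variance is 2/4.8 = 0.4167σ². The ratio is 0.4167/0.400 = 1.04, whichever order is left out.
- *Simple randomisation*, enumerating all 6⁵ = 7,776 draws: mean ratio 1.33, median about 1.2, 90th percentile about 2.0. No draw beats the list.
- *Non-estimable draws.* One treatment sits in the same phase for all five subjects with probability 9 × (1/3)⁵ − 12 × (1/6)⁵ = 0.0370 − 0.0015 = 0.0355. The second term corrects for multiple counting when all five orders are identical.
- *Five distinct orders arising by chance*: 6·5·4·3·2/7,776 = 9.3%.

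Reduction in mean variance: 1 − 1.04/1.33 ≈ 22%.

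**2. Both groups in one model, shared period effect, treatment effects by group.**

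- *Five distinct orders in each group.* The within-group information is 5 − 1/10 = 4.9 and the cross-group term has size 1/10. The variance is 2 × 4.9/(4.9² − 0.1²) = 9.8/24 = 0.4083σ², ratio 1.02 for every pair of lists.
- *Simple randomisation*, all pairs of allocations: mean ratio 1.16, non-estimable in about 0.05%.

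Reduction: 1 − 1.02/1.16 ≈ 12%.

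**3. Period not fitted, linear drift.** Let D be the phase 1-to-3 shift in within-subject SDs, so the drift per phase is d = D/2. Over the six orders the difference in position between two treatments is ±1, ±1 or ±2, with mean square (1+1+1+1+4+4)/6 = 2.

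- *Simple*: the extra variance is 2d²/n, so the ratio is 1 + d² = 1 + D²/4.
- *Five distinct orders*: the position differences of all six orders sum to zero, so only the missing order contributes, and the ratio is 1 + d²/5 = 1 + D²/20.

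| D (SD) | Simple | Five distinct |
|---|---|---|
| 0 | 1.00 | 1.00 |
| 0.5 | 1.06 | 1.01 |
| 1.0 | 1.25 | 1.05 |
| 1.5 | 1.56 | 1.11 |

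**4. Fewer completers, period fitted.**

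| Completers per group | Model | Simple | Distinct |
|---|---|---|---|
| 4 | Alone | 1.38 (10% non-estimable) | 1.13 |
| 4 | Shared period | 1.23 | 1.06 |
| 3 | Alone | 1.39 (28% non-estimable) | 1.36 |

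At three completers the mean variance is nearly the same. The gain is mainly that non-estimable allocations are avoided.

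**5. Price of the period term.** Expected 95% CI half-width without drift, in within-subject SDs:

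- *Alone*: simple without period 1.414 (8 df), distinct with period 1.515 (6 df), about 7% wider.
- *Shared*: simple without period 1.320 (16 df), distinct with period 1.346 (14 df), about 2% wider.

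By simulation, the list with a period term gives the narrower interval only above a phase 1-to-3 shift of about 0.75–0.8 SD (alone) or 0.4 SD (shared).

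**The case against.** The strongest case against is that the documents name no period term and give no evidence of drift. With neither, the list gains nothing. If the list is adopted together with a period term, the interval is slightly wider than under the plan as written unless drift exceeds the break-even values. If the list is adopted without a period term, the estimate is more precise under drift but the reported interval does not narrow. All of this stands, and it makes the gain conditional. It does not turn the list into a loss: at five per group, under the same analysis, no simple draw has lower variance with period fitted, and expected error without a period term is equal or smaller. The price in degrees of freedom belongs to the model, not to the list.

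Predictability also counts. After four subjects the fifth order is one of two, so a guess is right 50% of the time instead of 17%. Because the control phase is unmedicated, its position is visible. In 3 of the 15 possible remaining pairs (20%) the fifth subject's control position is certain to someone who knows the rule and the first four orders. This matters little, since every subject receives all three phases.

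Three stronger readings are tempting and not supported.

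- *That Aim 1c is biased or underpowered.* Simple randomisation is valid, and the documents make no power claim for Aim 1c.
- *That the figures for a group analysed alone (1.33, 3.5% non-estimable) are the general loss.* They apply only if period is fitted separately in each group. With a shared period effect the loss is about half that.
- *That the same change is needed in Aims 1b, 2 and 2a, which use the same wording.* Aim 1b states no sample size, Aim 2a is an outpatient option within Aim 2, and the table for Aim 2 lists 25 subjects, so the figures for groups of five do not carry over.

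**Conclusion.** The point holds as an optional, low-cost precision refinement, provided that period is fitted or real drift occurs. Under a shared period effect, five distinct orders per group lower mean contrast variance by about 12%; for a group analysed alone, by about 22%. Without a period term, the gain depends entirely on a drift that the documents do not quantify, and it is nil when there is none.

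The figures rest on reading simple as independent draws from the six orders, on five completers per group with the list used from the first subject, and, for the shared-period result, on the same period effect and residual variance in stone formers and healthy subjects. The documents neither support nor contradict that last assumption.

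**What to change.** If Aim 1c randomisation has not started, replace the simple scheme in the Aim 1c study protocol paragraph with a concealed, pre-drawn list of five distinct orders in random sequence, one list for stone formers and one for healthy subjects, held by someone not involved in enrolment. If it has started, use such a list for the remaining subjects and expect a smaller gain.

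State in one sentence whether period is fitted in Aim 1c. That choice is for the trial statistician. A shared period term protects against drift but costs two error degrees of freedom, with the price in interval width shown above.

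The cost is two short lists and that sentence, plus the partial predictability of the last order.

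### Aim 1c is labelled double-blind and placebo-controlled, but its listed control phase has no medication; the two statements must be reconciled

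*Combined protocol and SAP*

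**What the plan says.** The study protocol paragraph under Aim 1c Outpatient Study opens: "In this double-blind, placebo-controlled, crossover study, each subject will undergo 3 phases". The phase list that follows has three entries:

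- a: "Control, no medication"
- b: "Potassium Citrate 5mEq 1 pill, 2 times a day"
- c: "Potassium Citrate 10mEq, 1 pill, 2 times a day"

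Apart from the label, the Aim 1c text mentions no placebo or dummy pill, and it says nothing about how the tablets look.

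The other aims differ. Under Study Medications, Aim 1 gives "3 tablets twice daily of matching placebo during the PBO phase" and "two 10 mEq KCit tablets and one placebo tablet twice a day during the KCit phase", and describes "placebo tablets similar in appearance and size to the active medication tablets". Aim 1b lists a placebo phase and adds a placebo pill to its lower citric acid phase. Aims 1a, 2 and 2a each name a placebo among their phases.

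The objectives under Specific Aims call both metabolic studies placebo-controlled, and add Aim 1c to the first of them.

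**The concern.** A label of double-blind and placebo-controlled tells the reader that a subject cannot tell control from active treatment, and that the comparator accounts for the act of taking pills. A phase with no pills does neither. If Aim 1c runs as listed and is reported under its label, the design is misdescribed for the comparisons with control. Those comparisons bear most directly on the stated goal: a modest rise in urinary citrate without a pH change that cancels its benefit.

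The urine measures themselves come from a laboratory, so a subject's knowledge of the phase cannot act on the assay. What remains is behaviour at home: keeping to the instructed diet and fluids, and completing the 24-hour collection.

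There is also a practical problem. Staff who read the protocol cannot tell whether to dispense a placebo in the control phase or nothing.

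**Working it through.** There is no plan figure to reproduce: Aim 1c states no alpha, power, effect size or standard deviation. The check counts pills per day from each phase list (pills per intake × intakes per day) and compares phases within each aim.

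| Aim | Control phase | Second phase | Third phase |
|---|---|---|---|
| 1 (Study Medications) | placebo: 3 × 2 = 6 | citric acid: 3 × 2 = 6 | potassium citrate: (2 + 1 placebo) × 2 = 6 |
| 1b (phase list) | placebo: 3 × 3 = 9 | citric acid: (2 + 1 placebo) × 3 = 9 | citric acid: 3 × 3 = 9 |
| 1c (phase list) | no medication: 0 | potassium citrate 5 mEq: 1 × 2 = 2 | potassium citrate 10 mEq: 1 × 2 = 2 |

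Differences between the Aim 1c phases:

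- a versus b: 2 − 0 = 2 pills a day, so the subject can tell them apart.
- a versus c: 2 − 0 = 2 pills a day, so the subject can tell them apart.
- b versus c: 2 − 2 = 0, so the pill count reveals nothing. Blinding is possible if the two tablets look alike.

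Unequal pairs: 2 of 3 in Aim 1c, 0 of 3 in Aim 1 and 0 of 3 in Aim 1b. In Aims 1 and 1b the placebo pills are what make the counts equal; Aim 1c lists none.

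The text supports two explanations:

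- *The label is the slip.* The sentence that carries it is the same as in Aims 1a and 1b, so it may have been carried over. The control entry is specific to Aim 1c.
- *The list is the slip.* The Aim 1c rationale refers to "the recently completed three phases of the study control, potassium citrate and citric acid in calcium phosphate stone formers". The comparator in Aim 1 was matching placebo, so the authors do use *control* loosely for placebo.

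Nothing else in the documents decides between them.

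Scale: up to five patients plus five healthy subjects, 5 + 5 = up to 10.

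**The case against.** The strongest reply is that this is a wording fault in a small pilot with laboratory outcomes, the same instructed diet and fluids in every phase, and no power claim. That is largely fair. It limits the stakes but does not remove the contradiction, because a change to the text is needed whichever statement is wrong.

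A reader might infer more than the documents support, in four ways:

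- *That Aim 1c certainly is unblinded, and that reporting it under its label would certainly misdescribe it.* If a placebo is in fact given, the label would be accurate. Only the inconsistency is certain.
- *That the comparisons with control are biased.* This would need subjects to change diet, fluids or collection because they know the phase. The documents neither show nor size that.
- *That the lack of a diet supplied by the Clinical Research Unit in Aim 1c belongs to this fault.* It is a separate feature and would remain with a perfect placebo.
- *That the 5 and 10 mEq tablets can be told apart.* Aim 1c does not state that they match, but Aims 1a, 1b, 2 and 2a do not restate matching either. It is described once, under Aim 1, and Aim 1c is presented as an extension of Aim 1.

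It is also fair to say that Aim 1c specifies no contrasts. Treating the comparisons with control as the main ones is a reading of its goal, and 5 versus 10 mEq bears on the choice of dose as well.

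**Conclusion.** The point stands as an internal contradiction. The label and the phase list of Aim 1c cannot both be right. If the list is followed, 2 of the 3 phase comparisons cannot be blind to the subject and have no placebo, and the third could be blinded only if the two tablet strengths look alike. This rests on reading *no medication* literally and on the absence of any placebo from the Aim 1c text. Blinding of laboratory staff is a separate matter: the pill count does not affect it, and the documents do not describe it.

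No size or direction of bias is claimed. The text should be corrected, but no powered conclusion depends on it.

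**What to change.** Reconcile the two statements in one of two ways.

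1. *If a placebo is intended:* list phase a as placebo, one pill twice a day so that the count equals that of phases b and c, and state that it matches the potassium citrate tablets in appearance, as Aim 1 does for its own tablets. Cost: a placebo that matches both strengths must be compounded. Aim 1 already describes a placebo similar to its 10 mEq tablets, so the added work may be confined to the 5 mEq tablet. If the two strengths look different, which is not stated, they must also be made alike.
2. *If no medication is intended:* delete the double-blind and placebo-controlled wording from Aim 1c, make clear in the objectives that placebo-controlled does not cover Aim 1c, and report it as a randomised-order crossover with an open no-treatment control. Cost: a wording change only. The downside is that Aim 1c cannot then be cited as blinded or placebo-controlled evidence.

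The choice is the sponsor's. If any subject has already been studied, the report should state which control was actually given.
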